2.5. Study Day and Relative Day

Study Day 1 refers to the date of first study medication intake (reference day). All efficacy and safety assessments at all visits will be assigned a day relative to this date.

The relative day for a visit is defined as:

$$reldy = visit\ day - reference\ day + 1$$

for visits on or after the reference day, and

$reldy = \text{visit day} - \text{reference day}$

for visits before the reference day, where the reference day is the start of study medication.

There is no 'Day 0'.

2.6. Baseline

The baseline record is derived as the last record before the first intake of the study drug. The baseline record will be duplicated and assigned to the treatment phase.

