11.8. Safety Analyses

Safety data will be presented descriptively. No statistical testing of safety data is planned. For safety, baseline is defined as the last assessment prior to the first intake of study drug.

Adverse Events

The verbatim terms used in the eCRF by investigators to identify AEs will be coded using the Medical Dictionary for Regulatory Activities. Treatment-emergent AEs are AEs with onset during the treatment phase or that are a consequence of a preexisting condition that has worsened since baseline. All reported AEs will be included in the analysis. For each AE, the percentage of

subjects who experience at least 1 occurrence of the given event will be summarized by treatment regimen. In addition, comparisons between treatment regimens will be provided if appropriate.

Summaries, listings, datasets, or subject narratives may be provided, as appropriate, for those subjects who die, who discontinue treatment due to an AE, or who experience a severe or an SAE.

Clinical Laboratory Tests

Laboratory data will be summarized by type of laboratory test. Reference ranges and markedly abnormal results (specified in the SAP) will be used in the summary of laboratory data. Descriptive statistics will be calculated for each laboratory analyte at baseline and for observed values and changes from baseline at each scheduled timepoint. Changes from baseline results will be presented in pre- versus posttreatment cross-tabulations (with classes for below, within, and above normal ranges). Frequency tabulations of the abnormalities will be made. A listing of subjects with any laboratory results outside the reference ranges will be provided. A listing of subjects with any markedly abnormal laboratory results will also be provided.

The laboratory abnormalities will be determined according to the criteria specified in the draft DMID pediatric toxicity tables (see [Attachment 1](#)) and in accordance with the normal ranges of the clinical laboratory if no gradings are available.

Electrocardiogram

The effects on cardiovascular variables will be evaluated by means of descriptive statistics and frequency tabulations. These tables will include observed values and changes from baseline at each scheduled timepoint (the predose ECG will be used as baseline). Frequency tabulations of the abnormalities will be made.

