2. GENERAL ANALYSIS DEFINITIONS

2.1. Visit Windows and Phase Definition

Figure 1: Schematic Study Overview: Option A

Abbreviations: LD: loading dose; MD: maintenance dose; RSV: respiratory syncytial virus.

- a. Subjects randomized to placebo will be subsequently randomized in a 1:1 ratio to the placebo regimen matching Regimen A or Regimen B.

Phases will be constructed as follows:

Trial phase	Start date	End date
Pre-screening	Date time of first assessment, taken as part of standard of care within 84 hours* prior to randomization	1 minute before start of screening phase
Screening	00:00 of the date of signing the informed consent	1 minute before the first study medication intake
Treatment	Date time of first study medication intake	Date time of last investigational medication intake + 72 hours
Follow-up	End of Treatment phase + 1 minute	Trial termination date (date of last contact) with timestamp 23:59.

*In order to account for “approximately” 72 hours prior to randomization

The last phase, whichever it is for a subject, always ends on 23:59 of the day of trial termination (last contact) in study 64041575RSV2004. Note a subject can volunteer for long-term follow-up, in this case the subject will be enrolled in study 64041575RSV2002.

Assessments will be assigned to phases based on their date time, seconds will be ignored. If the day part of the start date of the assessment is present but the time part is missing, the assessment will be allocated as if it started at 00:00h on the day of the assessment (unless for Adverse Events see details in section 6.1.1). If the day part of the end date of the assessment is present but the time part is missing, no formal imputation will be done, but these rules will only be applied in order to be able to allocate assessments to phases. The assessment will be allocated as if it happened at 23:59h on the day of the assessment.

As subjects do not always adhere to the protocol visit schedule, the following rules are applied to assign actual visits to analysis visits. Listed below are the visit windows and the target days for each visit.

All visits (regardless the investigated parameter) will be allocated to analysis visits based on the day relative to the start of study medication:

Target Day	Analysis visit (numeric version)	Analysis visit	Day Interval
$-\infty$	-1	Screening	≤ 1 ¹
1	0	Baseline	≤ 1 ²
1	1	Day 1	[1] ³
2	2	Day 2	[2]
3	3	Day 3	[3]
4	4	Day 4	[4]
5	5	Day 5	[5]
6	6	Day 6	[6]
7	7	Day 7	[7,9]

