6.2.1. Definitions

Unifying multiple laboratory values by standardization:

Since local labs are used, the SI-converted values will be harmonized for selected parameters using the following formula and using the phantom laboratory generalized lab norms (GLN) as proposed by Francis Ruvuna, David Flores *et al.*^[4]

$$y = (x - L_i) * \frac{U_{cs} - L_{cs}}{U_i - L_i} + L_{cs}$$

Where

- y = the transformed individual analyte value to a common standard laboratory reference range;
- x = the original value;
- L_i and U_i = lower and upper limits of normal for individual laboratory analyte;
- L_{cs} and U_{cs} = lower and upper limit for the selected common standard laboratory or phantom laboratory GLN

The following additional rule applies for standard normal ranges with zero as lower limit and local normal ranges with non-zero lower limit. Zero will be used as lower local limit in the formula if the previous mentioned requirement was met.

The harmonized values, with the phantom laboratory GLN, will be used during the analysis.

Toxicity grades and abnormalities for laboratory parameters:

Toxicity grades will be computed according to the DMID adult toxicity grading list (see attachment at the end of this document) based on the harmonized values, for the parameters with harmonized values. In case different grades are available for fasted/non fasted results, the results are assumed to be taken in the condition as specified in the protocol (i.e. not necessarily according to possible remarks indicating a deviation to this). If no condition is specified in the protocol, the non-fasting gradings should be used.

In case no toxicity grades are defined for any laboratory test, then non-graded abnormalities (high/low vs. normal range) will be used instead.

The worst grade over the whole observational period (treatment phase, follow-up phase and combination of treatment and follow-up) will be determined.

Emergent definition for toxicity grades and abnormalities

An abnormality (toxicity grade or abnormality based on normal ranges) will be considered emergent in a particular phase if it is worse than the baseline value. If the baseline is missing, the abnormality is always considered as emergent. A shift from “abnormally low” at baseline to “abnormally high” post baseline (or vice versa) is also emergent. The emergent definition is applicable in both, the treatment and follow-up phase.

In case of missing date or time parts

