6.2.2. Analysis Methods

Actual values and change from baseline will be summarized by treatment group at each scheduled time point.

A cross-tabulation of the worst toxicity/abnormality versus baseline will be presented per phase (Treatment phase, Follow-up phase) and for the combination of Treatment and Follow-up phase. This table will also show the number and percentage of subjects per worst toxicity/abnormality, the number and percentage of subjects per emergent worst toxicity/abnormality and the cumulative number of subjects per emergent toxicity/abnormality or worse.

Mean \pm SE graphs over time for the actual values and changes from reference will be generated for all tests performed.

A listing of abnormal individual subject hematology and clinical chemistry values from scheduled and unscheduled time points will be provided. This listing will include all other time points for the corresponding subject/parameter, and will include both the original and harmonized values.

Grade 2 or higher toxicity laboratory values will be listed separately.

Urinalysis results will be listed. Proteinuria and urine WBCs will be summarized.

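### SAP 2.6 copies the pre-dose laboratory record into the treatment phase, so the worst-grade counts and shift table for the treatment and combined phases include baseline and cannot show improvement

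*SAP*

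**What the plan says.** - **Baseline (SAP 2.6).** Baseline is the last record before first intake. The section then says: "The baseline record will be duplicated and assigned to the treatment phase". It gives no purpose for the copy and no exception.
- **Treatment phase (SAP 2.1).** It runs from first intake to "Date time of last investigational medication intake + 72 hours".
- **Worst laboratory grade (SAP 6.2.1).** "The worst grade over the whole observational period (treatment phase, follow-up phase and combination of treatment and follow-up) will be determined". Nothing limits this to post-baseline records. The corresponding rules in 6.3.1 (vital signs) and 6.5.1 (ECG) do refer to post-baseline measurements.
- **Emergent rule (SAP 6.2.1).** An abnormality "will be considered emergent in a particular phase if it is worse than the baseline value".
- **Outputs (SAP 6.2.2).** "A cross-tabulation of the worst toxicity/abnormality versus baseline will be presented per phase", and also for treatment and follow-up combined. "This table will also show the number and percentage of subjects per worst toxicity/abnormality"; emergent worst counts appear in the same table.
- **Protocol 11.8.** Laboratory changes are to be cross-tabulated with pre-treatment results against post-treatment results.
- **Grading list.** SAP 6.2.1: "Toxicity grades will be computed according to the DMID adult toxicity grading list", with a pointer to the SAP's own attachment. That attachment (Attachment 1) is the pediatric table. Protocol 11.8: "The laboratory abnormalities will be determined according to the criteria specified in the draft DMID pediatric toxicity tables".

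**The concern.** The worst-grade rule works by phase, and 2.6 has placed a pre-dose record in the treatment phase. A programmer who follows the text will let that record compete for the worst grade. The post-treatment axis of the shift table then contains the pre-treatment value, which is not the comparison that protocol 11.8 describes.

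This deserves attention because the protocol names the hematopoietic system as the target organ in animals (1.1.2) and reports three serious or severe hematological events in hospitalized RSV subjects (1.3.3). Inclusion criterion 6 admits out-of-range laboratory values that the investigator judges acceptable, so some children will have a graded value before the first dose. At stake are how far the worst-grade columns can be read as describing what happened after dosing, and whether a difference between arms in recovery could be seen in them.

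**Working it through.** The documents state no figure on this point, so there is none to reproduce. The check has five steps.

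**1. Which results change.** Let B be a child's baseline grade and M the highest post-dose grade in the phase.

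- As written, worst = max(B, M). With post-dose records only, worst = M.
- max(B, M) is never below B, so every cell of the shift table with worst below baseline is empty by construction.
- The two rules differ whenever M < B. If there is no post-dose record, the written rule returns B where the result should be missing.
- Emergent requires a grade above B. A copy of B is never above B, so emergent results cannot change.

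As a check, take grades 0 to 4 for one baseline and two post-dose values: 5 × 5 × 5 = 125 patterns. Both post-dose grades lie below B in 0 + 1 + 4 + 9 + 16 = 30 patterns, and in those 30 the worst grade changes. The emergent worst grade changes in 0 of 125. These are counts of patterns, not probabilities.

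The copy goes to the treatment phase only. The follow-up-phase worst grade and the by-visit values and changes are therefore untouched.

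**2. Size of the excess.** For a given grade or higher, let p_b be the baseline prevalence, r the share of those children who still have that grade after dosing, and e the incidence among the rest.

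- As written: p_b + (1 − p_b)e
- Post-dose only: p_b·r + (1 − p_b)e
- Excess: p_b(1 − r)

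Neither p_b nor r is in the documents, so both are assumed. Cells show percentage points, with subjects out of the 60 planned per regimen (SAP 1.2.1) in brackets.

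| p_b | r = 0.8 | r = 0.5 | r = 0 |
|---|---|---|---|
| 5% | 1 (0.6) | 2.5 (1.5) | 5 (3.0) |
| 10% | 2 (1.2) | 5 (3.0) | 10 (6.0) |
| 20% | 4 (2.4) | 10 (6.0) | 20 (12.0) |
| 30% | 6 (3.6) | 15 (9.0) | 30 (18.0) |

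At r = 1 the excess is zero throughout.

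**3. Effect on the comparison of arms.** Randomization makes p_b equal across arms in expectation. The difference between two arms is then:

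- As written: (1 − p_b)(e₁ − e₂)
- Post-dose only: (1 − p_b)(e₁ − e₂) + p_b(r₁ − r₂)

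The written rule drops the recovery term p_b(r₁ − r₂) and adds nothing in its place. With p_b = 20%, r = 0.5 in both arms, and e = 10% versus 5% (all assumed), the table shows 28% versus 24% as written and 18% versus 14% post-dose only. The difference is 4 points either way.

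**4. How few records the copy competes with.** After screening, the in-hospital schedule has hematology on Days 2, 7 and 14, and biochemistry on Days 7, 14 and 28. If the last dose falls on Day 5, the treatment phase ends on Day 8, but the Day 7 visit may take place as late as Day 9. In that case no scheduled biochemistry sample falls in the treatment phase, and the copied baseline can be the only record there.

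**5. Which grades are carried over.** Exclusion criteria 16 to 18 largely keep Grade 3 and 4 hemoglobin, neutrophil and platelet values out of baseline. Hematology carry-over is therefore mainly Grade 1 and 2. That list sets no comparable grade limit for chemistry.

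**The case against.** The strongest reply is that the SAP may not intend the copy to be a candidate at all. SAP 1 says the plan is to be read together with the protocol, and protocol 11.8 calls for pre- against post-treatment tables. SAP 2.1 starts the treatment phase at first intake, keeps Baseline as a separate analysis visit and restricts Day 1 to post-dose records. The copy may be there only so that displays over time have a starting point. This is a plausible account of the intent, but the SAP does not state it. Section 2.6 assigns the record to the phase without exception, and 6.2.1 lacks the post-baseline wording used in the two parallel sections.

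The limits on scope stand in full. Safety is descriptive with no testing planned, the baseline grade appears beside the worst grade in the cross-tabulation, and the emergent counts are in the same table.

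Three stronger readings are tempting, and the documents do not support them:

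- A reader might infer that pre-dose abnormalities are reported as treatment-emergent toxicity, or that only the emergent columns are right. The emergent rule excludes a copy of baseline, and the follow-up-phase and by-visit results are also correct.
- A reader might infer heavy dilution, for example incidences of 10% versus 5% with 20% abnormal at baseline shown as 28% versus 24%, a ratio of 1.17 instead of 2.0. All three inputs are assumed, and the calculation also takes on-treatment abnormality to be independent of baseline. Even so, the difference moves only from 5 to 4 points.
- A reader might infer that children will be graded on adult limits. The sentence points to the SAP's attachment, which is pediatric and age-banded, and no adult list is supplied.

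**Conclusion.** The point holds with a limited scope. Followed as written, SAP 2.6 and 6.2.1 put the pre-dose value into the non-emergent laboratory worst-grade counts and the worst-versus-baseline cross-tabulation for the treatment and combined phases. Those tables cannot show improvement and depart from protocol 11.8.

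The overstatement is p_b(1 − r): 1 to 30 percentage points for an assumed p_b of 5% to 30% with r from 0.8 to 0, and none if every baseline abnormality persists. The width of that range reflects the absence of both inputs from the documents. The copy adds the same expected background to each arm and creates no false drug signal; what it can hide is a difference in recovery. The adult wording in 6.2.1 is an inconsistency that is unlikely to change any grade.

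**What to change.** In SAP 6.2.1, add one sentence: worst grades and abnormalities per phase, and for the phases combined, use only records after first dose, and the duplicated baseline record from 2.6 is excluded. This brings the laboratory rule into line with the post-baseline wording already in 6.3.1 and 6.5.1. A child with no post-dose result in a phase then has a missing worst grade for that phase.

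In the same section, change the named grading list from adult to pediatric, so that it agrees with SAP Attachment 1 and protocol 11.8.

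The cost is one added sentence and one changed word. No new data or additional analysis is needed.

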3. INTERIM ANALYSIS AND DATA MONITORING COMMITTEE REVIEW

3.1. Interim Analysis

An Interim Analysis Committee will be responsible for performing the formal interim analysis and will consist of sponsor personnel who are not otherwise involved in the study. The IDMC will review the data and make recommendations to the Sponsor Committee, which will be responsible for identifying appropriate actions based on the recommendations of the IDMC.

Two types of interim analyses are distinguished: formal interim analysis and interim analyses performed by the IDMC only. The IDMC is described in Section 3.2, Independent Data Monitoring Committee, and Section 3, Overview of Study Design. At any formal interim analysis, the IDMC will also perform a data review.

The Interim Analysis Committee will be responsible for performing any formal interim analysis and will consist of sponsor personnel who are not otherwise involved in study activities. The first formal interim analysis will be performed when 36 subjects with ≤ 3 days of RSV symptoms have completed treatment or when 90 subjects with > 3 to ≤ 5 days of RSV symptoms have been enrolled and have completed treatment. The second interim analysis may be performed at the discretion of the sponsor when at least 120 subjects have completed treatment (or at least 60 subjects with ≤ 3 days of RSV symptoms), which may allow an analysis at the end of a season.

The following situations will be considered based on the results of any formal interim analysis: that the study is considered futile; that superiority can be concluded; that subjects with > 3 to ≤ 5 days of RSV symptoms at randomization may not achieve benefit (which may also be limited to ≤ 4 days of onset to symptoms); that the treatment duration needs to be increased to up to 10 days; or that the study should continue unchanged. In the case of the (unbinding) futility boundary or the superiority boundary being crossed, the IDMC may recommend early termination to the Sponsor Committee. If early superiority on the primary endpoint can be established, the study may be continued in order to accumulate data to allow the selection of the dose regimen or further substantiate the benefit-risk profile in this population; in this case the randomization ratio of active to placebo treatment may be altered for example, if dose selection is evident from the dose-response analysis, subjects randomized to active treatment may all receive the optimal dose. Alternative randomization ratios can be endorsed by the IDMC and implemented by the Sponsor Committee for Option A are 1:2:0, 1:0:2, 1:2:2, and 2:1:3 for the placebo, low dose, and high dose, respectively.

Results of the formal interim analyses can be used in interactions with Health Authorities.

3.2. Independent Data Monitoring Committee

An IDMC will be established to monitor data and will review data in an unblinded manner on a regular basis to ensure the continuing safety of the subjects enrolled in this study. The IDMC will review the data and make recommendations to the Sponsor Committee, which will be responsible for identifying appropriate actions based on the recommendations of the IDMC. Details are provided in the IDMC Charter.

The IDMC will consist of at least 1 medical expert in the relevant therapeutic area and at least 1 statistician, 1 of whom will chair the committee. The IDMC responsibilities, authorities, and procedures will be documented in the IDMC Charter. Other members may be required dependent on the nature of the interim analysis. The intent is to have the same IDMC monitoring this study as for Study ALS-8176-503 given their familiarity with the compound. The IDMC will make dose recommendations at the beginning of the study, which will help determine which design option is chosen.

The IDMC will review the PK and safety data at the timepoints specified in Section 3, Overview of Study Design, and will continue to assess the PK, safety, and (selected) efficacy data during the conduct of the study. The frequency of IDMC reviews will be detailed in the IDMC Charter. At any formal interim analysis, the IDMC will also perform a data review.

Given the challenges of ensuring study-site preparation in time to recruit for an acute seasonal infection like RSV and the delays caused by implementing an amendment during an RSV season, the duration of dosing of lumicitabine may be modified by recommendation of the IDMC based on the review of this study and data from other ongoing studies of lumicitabine. The duration of dosing if extended will not exceed 10 days and the doses will not exceed those resulting in an expected average JNJ-63549109 plasma AUC_{0-24h} of 20,000 ng.h/mL (or 25,200 ng.h/mL in whole blood), a limit that is 2.7-fold lower than the lowest systemic NOAEL exposure observed in nonclinical toxicity studies. If the IDMC determines that subjects with a duration of RSV symptoms of 5 days prior to randomization may not achieve benefit based on interim results, they may recommend that the time of onset of RSV symptoms to the time of randomization is reduced. In addition, if the IDMC determines that subjects with a duration of RSV symptoms longer than 5 days prior to randomization may achieve benefit, this duration may be increased to up to 7 days (ie, 7 days from symptom onset to randomization). If such modifications, including changes to the randomization ratio, are recommended by the IDMC and endorsed by the Sponsor Committee, these changes will be communicated in writing to investigators, health authorities, and IEC/IRB and may be implemented without amendment to this protocol. Sponsor personnel involved in this process will not be involved in the conduct of the study. Details are provided in the IDMC Charter.

